5.2 Handling of Study Conditions

Participants in both conditions will receive the study session content delivered by trained study therapists via telephone or video chat. Once the baseline assessment is completed and the participant has been randomized to the study condition, participants will be provided with the appropriate patient workbook or brochures and necessary information for participation in their assigned condition. Study therapists will explain the nature of the sessions to the participants and will answer any questions they may have regarding how the remaining sessions will be completed remotely. In addition, all participants who complete the first remotely delivered session in either condition (PPMI or ECU) will receive \$40 to offset any potential costs that they might incur due to the use of their phones (minutes or data). It will be the responsibility of the study therapist assigned to the participant to set an appropriate therapy schedule (dates and times for therapy sessions) and to communicate that schedule and any changes to that schedule with the participant. In general, and where possible, study sessions should be scheduled at the beginning of treatment and should be set up on a consistent basis to encourage completion (e.g. scheduled Tuesday and Thursday at 2:00pm for the next 4 weeks). During the delivery of both conditions, study therapists will follow the therapy manual for each condition and if using video chat, the therapist may display the condition materials on the screen. All procedures (check-in forms, session activities, handouts, feedback forms, etc.) will be delivered for each session according to the manual guidelines. Deviations from delivering the approved session content -in the order intended- should be avoided unless the deviation is necessary for the safety and well-being of the participant (e.g. if a participant reports

acute, debilitating withdrawal symptoms at the beginning of the session, session content may be diverted until it is clear the participant is safe). Any session content or procedural deviations that occur during the therapy sessions will be communicated to the project managers and/or clinical supervisor for documentation in the trial record. Further details of completing study intervention accountability records will be provided in the study Manual of Operations (MOP).

5.3 Concomitant Interventions

The PPMI and EUC conditions are designed to augment current OUD treatment, not to take the place of current treatment. Therefore, due to the nature of the study sample (chronic pain patients with OUD on buprenorphine), it is expected that participants may be engaged in a variety of other treatments, either therapeutic or pharmacologic in nature, during the duration of the study. Participation in this study will not be restricted by any additional treatments they may be receiving.

5.3.1 Allowed Interventions

Participants may continue to take any prescribed medications including medications for physical health conditions, mental health conditions, or medications for the treatment of OUDs, including buprenorphine during their study participation. Participants may continue to take prescription opioid medications and/or other prescription medications for the treatment of a substance use disorder (e.g. disulfiram). Participants may be required by their treatment provider to participate in some form of outpatient counseling (including CBT treatment) or recovery self-help groups as a requirement of remaining on buprenorphine through the treatment clinic. Because remaining in buprenorphine treatment is the primary outcome in this study, involvement in these auxiliary treatments will be allowed. Data will be collected during all study assessments to capture the scope and frequency of the participant's involvement in additional treatment activities during their time on study. Participants may also be receiving medical care or treatment for a pain condition (e.g. physical therapy, acupuncture, etc.) while in the study. When possible, treatment records at the study sites will be reviewed to gather information regarding participant treatment involvement during the study. Where treatment records are not available or accessible through a signed release of information, participant self-report of treatment involvement collected at follow-up will be used to track treatment involvement.

5.3.2 Required Interventions

There are no required interventions a participant must engage in while in the study. Prior to enrollment in the study, participants must be actively participating in buprenorphine treatment for the treatment of an OUD. While actively taking the medication is a requirement for study enrollment, discontinuing buprenorphine treatment will not result in the termination of study participation.

5.3.3 Prohibited Interventions

There are no prohibited interventions associated with study participation.

5.4 Adherence Assessment

For this study, adherence to the study intervention condition (PPMI) will be defined as participation in at least 50% of the condition sessions. This would equate to participating in at least 4 of the 8 study sessions. The PPMI condition is designed to be progressive in nature, with each

session building on materials learned or discussed during previous sessions. Because of this, receiving at least 4 sessions of material in the PPMI condition related to chronic pain management and buprenorphine adherence/retention, will be considered an adequate dose. Likewise, adherence to the study control condition (EUC) will also be defined as participation in at least 50% of the condition sessions, or 1 of 2 study sessions. Due to the nature of the study (a behavioral therapy intervention study), participants will not be required to attend study sessions and will not be compensated for their involvement in the individual sessions. Study therapists and research staff will discuss the benefits of remaining engaged in the study treatment during the initial study meeting, however participants will be free to discontinue the study sessions at any time. Study therapists will make reasonable attempts to contact the participant should they disengage from the sessions. Participants will only be allowed to complete study sessions up to 6 weeks post enrollment. This cutoff was determined to allow for adequate time for the participant to complete the 1-month follow-up assessment. Participants will be eligible to participate in all follow-up assessments regardless of study session participation.

6. STUDY PROCEDURES

Below please find the study Schedule of Events. The eligibility screening survey is expected to take approximately 5 minutes to complete. We expect the initial enrollment assessment will take approximately 2 hours to complete, while the remaining follow-up assessments will take approximately 90 minutes to complete. This length is comparable to research assessments conducted by this research team in multiple projects. In these previous instances, patients were typically able to complete the entire assessment without problems. In the occasional case where a patient became tired or irritable, the assessment was split into two sessions and completed within the next couple of days. This technique was highly successful and did not result in problems with missing data. We will utilize this same strategy in this study and do not expect problems due to participant burden. We expect the weekly surveys will take approximately 5-10 minutes to complete.

6.1 Schedule of Evaluations

Assessment	Screening	Baseline, Enrollment, Randomization	PPMI or EUC Sessions: Treatment Visits	Weekly surveys	1-month follow-up	3-month follow-up	6-month follow-up	9-month follow-up	12-month follow-up
Electronic or Verbal Consent for eligibility screening	X								
Demographics – age, sex, recruitment location	X								
Self-reported pregnancy	X								
Access to telephone	X								
Numeric Rating Scale for Pain Intensity (NRS-I)	X			X	X	X	X	X	X
Buprenorphine treatment involvement	X	X		X	X	X	X	X	X
Rapid Opioid Dependence Screen (RODS)	X								
Inclusion/Exclusion Criteria	X	X							
Informed Consent		X							
The Structured Clinical Interview for DSM-5 Disorders: Substance Use Disorders Section, Opioids only (SCID-5)		X							
TimeLine Follow-Back (TLFB)		X			X	X	X	X	X
Legal Questions		X			X	X	X	X	X
Treatment Services Review		X			X	X	X	X	X
Urine Drug Screen		X			X	X	X	X	X

Assessment	Screening	Baseline, Enrollment, Randomization	PPMI or EUC Sessions: Treatment Visits	Weekly surveys	1-month follow-up	3-month follow-up	6-month follow-up	9-month follow-up	12-month follow-up
Enrollment/Randomization		X							
Demographics & Military History		X							
Veterans RAND 12 Item Health Survey (VR-12)		X			X	X	X	X	X
Barriers to Treatment		X			X	X	X	X	X
Buprenorphine Diversion		X			X	X	X	X	X
Beliefs about Buprenorphine treatment		X			X	X	X	X	X
Brief Pain Inventory – Short Form (BPI-SF)		X			X	X	X	X	X
Chronic Pain Acceptance Questionnaire (CPAQ)		X			X	X	X	X	X
Self-efficacy to Manage Chronic Conditions – Pain		X			X	X	X	X	X
Confidence Questionnaire		X		X	X	X	X	X	X
Patient Health Questionnaire (PHQ-9)		X			X	X	X	X	X
General Anxiety Disorder (GAD-2)		X			X	X	X	X	X
Alcohol Use Disorders Identification Test –Concise (AUDIT-C)		X			X	X	X	X	X
Injection drug use and overdose history		X			X	X	X	X	X
Social Support		X			X	X	X	X	X
Reasons for Leaving Treatment Questionnaire (RLTQ)					X	X	X	X	X
Symptoms and Behavior Questions				X					
Post-treatment survey (1 time)					X				

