
Section 6.1 “Schedule of Events” for a list of specific measures and tasks). Documentation of the informed consent will be entered into study tracking logs and appropriate case report forms will be completed.

Since informed consent is an ongoing process, should the study protocol be amended in a way that may impact study participation, participants may be required by the IRB to provide consent again to continue participation. All changes to the consent forms will be approved by UM IRBMED and VA Ann Arbor IRB and any additional entities necessary prior to re-consenting of any participants. When an in-person baseline assessment is conducted, there may be temporary transportation of paper informed consent forms, paper data collection instruments, and other paper administrative forms (e.g. case report forms, Locator forms, payment receipts, etc.) from treatment clinics and/or community locations where data is collected to the research offices. Paper forms will be transported through the use of a lockable carrying cases and kept with study staff at all times. Because consent forms, locator forms, and payment receipts will contain identifying information, they will be kept in locked file cabinets in research offices. These file cabinets will be separate from study data. All electronic consent forms will be stored on a secure server. Research records, including consent forms, and/or identifiers will be retained in accordance with the NIH Records Management Schedule.

Screening

Participants will complete an electronic and/or verbal consent, depending on recruitment type (See Section 4.3 “Study Enrollment Procedures” above), prior to answering eligibility questions. The eligibility screening will involve the collection of data through survey questions (please Section 6.1 “Schedule of Events” for specific measures) and should take approximately 5 minutes to complete. Survey questions related to the inclusion/exclusion criteria will be asked in the following order:

- Basic demographic information (age, biological sex, gender, state and country residency)
- Self-reported pregnancy (*dichotomous yes/no question*)
- Recruitment location (*multiple response options*)
- Accessibility of telephone (*dichotomous yes/no questions*)
- Average pain score within the past 3 months (*measured by the NRS-I*).

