 - The Numeric Rating Scale of pain intensity (NRS-I) is an 11-point numeric rating scale (0 = no pain, 10 = worst pain imaginable) widely used in medical settings to assess global pain intensity.
- Current buprenorphine prescription (*multiple response options*)
- Route of administration for buprenorphine medication (*multiple response options*)
- Opioid use disorder diagnostic screen (*measured by the RODS*).
 - The Rapid Opioid Dependence Screen (RODS) is an 8-item measure designed to screen for opioid dependence.

Once the participant completes the eligibility survey, responses will be reviewed to assess for potential eligibility. For those participants who are ineligible, their participation in the study will be complete at this time. No identifiable information or contact information

will be collected from those participants who screen ineligible, or from those participants who screen eligible but report no interest in continuing on with the research study. All eligibility criteria will be confirmed, including most recent buprenorphine treatment episode start date and self-reported use of prescribed buprenorphine within 10 days of the enrollment interview, with the participant prior to the participant being enrolled in the study. Participants will have 60 days from the date the eligibility screening is completed to schedule and complete the baseline enrollment assessment. Eligible participants who do not complete enrollment within that time frame will be considered to have declined to participate in the full RCT.

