Once generated, documents that include the randomization sequence will be password protected to avoid inadvertent access by research staff involved in the enrollment process. Research staff will contact the project managers to randomize all participants using the randomization sequence provided by the biostatistician. The randomization process will be overseen by the project managers who will be notifying the research therapists of assigned

condition for specific participants at the completion of all baseline assessments. Randomization will occur once the baseline enrollment assessments are complete, which will take place no later than 60 days following the completion of the eligibility screening survey. Initiation of the study treatment condition (either PPMI or EUC) will occur immediately following randomization, when possible. Study sessions delivered via telephone or video chat should take place within one week of study enrollment and randomization for those in the PPMI condition and within two weeks of study enrollment and randomization for those in the EUC condition in order to provide enough time for all sessions to be completed within the 4-6-week treatment window.

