For **Secondary Aim 1**, retention on buprenorphine treatment will be measured using data collected during the Time Line Follow Back over 12-months. The Timeline Follow-Back Assessment of Substance Use (TLFB) protocol examines daily alcohol and other drug consumption over specified time intervals (e.g., 90-180 days) using monthly calendars. Several studies have demonstrated the reliability and validity of this method of assessing alcohol use using test-retest and convergent methodologies, and a recent study supports the reliability and validity for assessing drug use. Utilizing the TLFB, we will be able to collect alcohol use, drug use, and buprenorphine treatment data (including number of days the participant has taken their medication) throughout the entire follow-up period (12-months post study enrollment).

The secondary outcomes are hypothesized to meet the assumptions of continuous variables, and we will consequently use t-tests to make comparisons. If, however, the distribution of a measure is skewed, alternative modeling strategies will be used. In all analyses, we will use an intent-to-treat framework. Pain level will be measured using the Numeric Rating Scale for Pain Intensity (NRS-I), an 11-point numeric rating scale (0 = no pain, 10 = worst pain imaginable). All participants will be asked to rate their usual and worst pain over a specified time frame (e.g. past week, past 3 months, since last visit, etc.) We will take the average of these ratings as the primary measure of pain intensity. Participants will complete the NRS-I during all assessments, including the weekly surveys. Frequency of substance use will be measured using the Time Line Follow Back Interview (TLFB), a calendar-assisted structured interview that provides the participant with temporal cues to increase the accuracy of recall. Participants are asked to recall how much they drank or used any other controlled substances on each day during the specified time frame, starting with the most recent day and progressing back one day at a time. The interviewer-administered instrument has demonstrated test-retest reliability of greater than 0.86. Percent days abstinent from alcohol and drugs will be used as the primary measure of substance use at

each assessment time point (baseline enrollment assessment and 3- and 12-month follow-up assessments).

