9.5.2 Secondary Outcomes

The **secondary outcomes** of interest are pain level, pain-related functioning, and frequency of substance use. We hypothesize that participants receiving the PPMI condition (intervention condition) will report less pain, an increase in pain-related functioning, and lower frequency of substance use over the 3-month (Secondary Aim 2) and 12-month (Secondary Aim 3) follow-up period when compared to the EUC condition (control condition).

These outcomes for both **Secondary Aims 2 and 3** will be measured in the following ways:

- **Pain level** will be measured using the Numerical Rating Scale for Pain Intensity (NRS-I), which will be collected at all time-points. For each follow-up time point, we will subtract the baseline value to obtain a change score. For this study, a clinically significant change in pain level will be operationalized as a 30% reduction of pain, which would equate to change of 2 points on a 0 to 11 pain intensity numerical scale such as the NRS-I.
- **Pain-related functioning** will be measured using the pain interference subscale of the Brief Pain Inventory – Short Form (BPI). The BPI Short Form is a widely used, validated measure that assesses both pain level and the impact pain has on functioning over the past 24 hours. For each follow-up time point, we will subtract the baseline value to

obtain a change score. For this study, an increase in pain-related functioning will be operationalized as a reduction in the pain interference scale scores over time.

- **Frequency of substance use** will be measured using the TLFB, which will be collected at all follow-up time-points. During this administration, the participant will be asked to recall their alcohol and drug use since the previous follow-up time point. Percent days abstinent from alcohol and drugs will be used as the primary measure of substance use at each assessment time point (baseline, 1-, 3-, 6-, 9-, and 12-month follow-up assessment).

To accomplish **Secondary Aim 4** (qualitative interviews for rapid implementation), a random sample (n=20) of participants who completed the PPMI condition will be interviewed in addition to a sample (n=15) of buprenorphine providers/clinic staff.

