means and standard deviations for these outcomes at baseline, 1-, 3-, 6-, 9-, and 12-months, as well as change scores from baseline for the two groups. We hypothesize that participants randomized to the PPMI will have less pain, better functioning, and lower frequency of opioid use at follow-ups compared to EUC. These secondary outcomes are hypothesized to meet the assumptions of continuous variables, and we will consequently use t-tests to make comparisons. If, however, the distribution of a given outcome measure is skewed, alternative modeling strategies will be used. We will use a linear mixed-effects model and estimate the treatment effect as the difference in the time-averaged changes from baseline in pain levels (using the NRS-I) and in pain-related functioning (using the BPI) over the course of follow-up (namely, at 3-months for secondary aim 2 and at 12-months for secondary aim 3). Because reduction in pain is of key interest, the analysis will model change-scores from baseline in the response variable as the dependent variable, and the independent variables will include the baseline values of the response variable, time in months since randomization and the treatment group indicator. The parameter estimate of the treatment group indicator will estimate the time-averaged treatment effect. If the graphical exploration (described above) shows potentially differential linear decrease in pain over time, we will include an interaction of time by treatment group indicator to model and test for this. For frequency of substance use, we will first assess the distribution of measures collected to assess alcohol use, illicit drug use and prescription opioid medication use to determine whether a summary or composite measure of each of these may represent the use or misuse more appropriately. For example, illicit drug use will be obtained as the number of days the participant used each of multiple drugs, and thus we may consider combining the days of any of the illicit drug use. We will also combine the alcohol and drug use data obtained using TLFB interviews as the percent days abstinent from alcohol and drugs during the past 30 days at each assessment time. We will then check the distribution of the substance use and prescription medication misuse (measured using the TLFB), and unless the data are highly skewed, we will use a linear mixed-effect model to test the hypothesis and to estimate the treatment effect as the difference in the time-averaged changes from baseline in these outcome measures over the course of the 12-month follow-up period.

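### The schedule omits the NRS-I at the baseline visit while the outcome text says it is collected at every assessment, so the baseline value for the pain change score is undefined

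*Combined protocol and SAP*

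**What the plan says.** **Outcome and model.** Pain level on the NRS-I is a secondary outcome for Secondary Aims 2 and 3. Section 9.5.2 states: "For each follow-up time point, we will subtract the baseline value to obtain a change score". Section 9.6 models the change score and adds that "the independent variables will include the baseline values of the response variable". The baseline rating is therefore used twice.

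**Schedule (6.1).** The row that begins "Numeric Rating Scale for Pain Intensity (NRS-I" is marked at screening, in the weekly surveys and at 1, 3, 6, 9 and 12 months. The cell for the baseline, enrollment and randomization visit is blank. Section 6.2.1 refers staff to this schedule for what to administer at the baseline assessment.

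**Outcome text.** Section 9.5.1 says "Participants will complete the NRS-I during all assessments, including the weekly surveys", and 9.5.2 likewise has the NRS-I collected at all time-points.

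**Screening rating.** The eligibility survey in 6.2.1 asks for "Average pain score within the past 3 months", and section 4.1 requires a score of at least 4. On timing, 6.2.1 says "Participants will have 60 days from the date the eligibility screening is completed to schedule and complete the baseline enrollment assessment", and 6.2.2 places randomisation "no later than 60 days following the completion of the eligibility screening survey".

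**Scoring.** Section 9.5.1 defines pain intensity as the average of usual and worst pain over a time frame that it gives only by examples.

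**The concern.** A change-from-baseline outcome needs one defined baseline. Here the operative table and the outcome text disagree on whether that value is collected, and no sentence settles which rating is meant.

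If sites work from the table, the screening rating becomes the baseline by default. It has four weaknesses in that role:

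- It may precede randomisation by up to 60 days.
- It looks back 3 months, so its window can reach about 5 months before randomisation. Participants began buprenorphine within the past 6 months (4.1), and pilot participants said that it reduced their pain (2.1).
- It may be scored differently from follow-up: average pain at screening, against the mean of usual and worst pain for the outcome.
- It was used to select participants, so the ratings that follow will tend to be lower with no treatment effect.

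The first three can weaken the correlation with follow-up and so reduce precision. The fourth distorts within-arm change and the proportion reaching the 2-point reduction that 9.5.2 treats as clinically significant.

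**Working it through.** The plan gives no power, SD or sample-size figure for the NRS-I, so there is no figure of its own to reproduce.

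**1. Is the blank cell real?** The header has 10 cells and the NRS-I row has 10 cells. The next row (buprenorphine treatment involvement) and the BPI-SF row parse in the same way, and both carry a mark at baseline. The blank is not an extraction fault.

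**2. Could another rating serve?** The weekly surveys start after the baseline assessment (6.2.4), and randomisation follows as soon as baseline data collection is complete (6.2.2). Under the schedule, screening is the only NRS-I taken before randomisation.

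**3. Precision.** Let r be the correlation between baseline and one follow-up, with equal SDs at both times. The values of r are assumptions: 0.6 for a rating at the baseline visit, and 0.4 to 0.5 for the screening rating.

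- Baseline-adjusted variance is proportional to 1 − r².
  - r = 0.5: (1 − 0.25)/(1 − 0.36) = 0.75/0.64 = 1.17, and √1.172 = 1.083.
  - r = 0.4: (1 − 0.16)/(1 − 0.36) = 0.84/0.64 = 1.31, and √1.3125 = 1.146.
  - Variance rises 17 to 31%, and intervals widen by about 8 to 15%.
  - With the 160 participants expected to give follow-up data (section 4), this equals analysing 160/1.172 = 137 down to 160/1.3125 = 122.
- Unadjusted change-score variance is proportional to 2(1 − r).
  - r = 0.5: 1.0/0.8 = 1.25.
  - r = 0.4: 1.2/0.8 = 1.50.
  - This applies to the t-tests in 9.6, not to the mixed model that adjusts for baseline.

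Both sets of ratios are for a single follow-up. The time-averaged effect in 9.6 would give different values.

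**4. Selection.** A rounded 0 to 10 rating was simulated with entry at 4 or more and no treatment effect. The assumed inputs were a screened-population mean of 4 to 6, an SD of 2.0 to 2.5 and a test-retest correlation of 0.5 to 0.8. None of these is in the documents.

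- The mean rating fell by 0.1 to 0.8 points (0.09 to 0.84 across the settings).
- Between 13% and 39% of participants dropped by 2 points or more. Part of that share is ordinary test-retest variation that any baseline would show, so it is not all due to selection.

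Screening precedes randomisation, so the effect is expected to be the same in both arms.

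**The case against.** The strongest reply is that a single blank cell should not override the text. Sections 9.5.1 and 9.5.2 both say that the NRS-I is collected throughout. Section 6.2 has the follow-up assessments mirror the baseline one, and the NRS-I is in every follow-up. The Précis and 9.6 promise baseline means and SDs. Section 6.2.2, listing the baseline instruments, introduces the BPI as additional to the NRS-I. Eligibility is also rechecked before enrollment, so pain may be asked again.

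Much of this stands. A reader might infer from the schedule that the trial has chosen a screening rating as its baseline. The documents do not support that: no sentence says so, and most of the text points the other way. The text does not remove the contradiction, however. The mention in 6.2.2 refers back to an earlier list, which is the screening list. Section 6.2.4 says that follow-ups combine screening-survey and baseline measures, which fits an NRS-I held only at screening. And the schedule is the table to which staff are sent.

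Three further objections are fair and are accepted:

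- The correlations are assumed. Follow-up ratings might themselves use 3-month recall, so the loss of correlation is not established.
- Sixty days is a maximum, and no typical gap is given.
- Secondary Aims 2 and 3 compare arms, and selection at screening does not bias that comparison.

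**Conclusion.** The supported finding is an internal contradiction in a table that staff use, which leaves the baseline of a secondary outcome undefined. Pain is not labelled a key secondary outcome. Section 9.6 does, however, justify the change-score model with "Because reduction in pain is of key interest", so the point is more than clerical.

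The consequences depend on the schedule being followed as printed. In that case precision could fall, by the illustrative 8 to 15% in interval width if the assumed correlations hold. Within-arm improvement and the share meeting the 2-point criterion would look too favourable in both arms. A reader might go further and infer a biased treatment effect. That does not follow, because the screening rating is taken before randomisation and affects both arms alike. The primary retention outcome is not touched.

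**What to change.** Reconcile 6.1 with 9.5.1 and 9.5.2:

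- Mark the NRS-I in the baseline column, to be completed before randomisation, with the same usual and worst items and the same recall window as the follow-up assessments. Section 9.5.1 should state one window instead of examples.
- State in 9.5.2 and 9.6 that this rating is the baseline value for both the change score and the covariate.
- For anyone enrolled without it, name the screening NRS-I as the baseline for the change score. As an option, add the baseline BPI-SF pain-level items as a further covariate, noting their 24-hour recall (9.5.2). They cannot replace the NRS-I in the subtraction.

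The source of the baseline should be settled before any outcome analysis. The cost is one or two items in a 2-hour assessment, one mark in the schedule, and a few sentences of text.
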